## B) 3 month evaluation:

- e. Isometric knee extension at 60 degrees on involved and involved side.
  - i. Quadriceps deficit= 100- (Knee extension peak torque involved/knee extension peak torque uninvolved)
- f. Isometric knee flexion at 60 degrees on involved and uninvolved side
  - i. Hamstring Deficit= 100- (Knee flexion peak torque involved/knee flexion peak torque uninvolved)
- g. Isometric hip extension at 60 degrees on involved and uninvolved side
  - i. Hip extension deficit= 100- (Hip extension peak torque involved/hip extension peak torque uninvolved)
- h. Quad hypertrophy will be measured by thigh circumference measurement.
  - i. Measured at 10cm above the superior pole of the patella bilaterally.

- i. Y Balance Test (all measures taken bilaterally)
  - i. 3 trials anterior reach involved and uninvolved (cm)
  - ii. 3 trials posteromedial reach involved and uninvolved (cm)
  - iii. 3 trials posterolateral reach involved and uninvolved (cm)
  - iv. Anterior reach difference= Max anterior reach involved Max anterior reach uninvolved
  - v. Posteromedial reach difference= Max posteromedial reach involved- Max posterior reach uninvolved
  - vi. Posterolateral reach difference= Max posterolateral reach involved-Max posterolateral reach uninvolved.
  - vii. Involved and Uninvolved Composite score= (Max anterior reach+ Max posteromedial reach + max posterolateral reach)/(3\*Limb Length) \*100.
- j. 8" Anterior Stepdown Test (measures taken bilaterally)
  - i. Involved repetitions= Max repetitions in 1 minute.
  - ii. Uninvolved repetitions= Max repetitions in 1 minute.
- k. Elevated single leg bridge test completed with a 12" box (all measures taken bilaterally)
  - i. Involved repetitions= Max repetitions in 1 minute.
  - ii. Uninvolved repetitions= Max repetitions in 1 minute.
- 1. Half kneeling dorsiflexion distance (all measures taken bilaterally)
  - i. Half kneeling difference = half kneeling involved- half kneeling non involved

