### **Background**

Exercise training with blood flow restriction (BFR) is a technique increasingly used in physical therapy and rehabilitation settings as an alternative to heavy load resistance exercise, and has increased in popularity in clinical and healthy populations over the last two decades. Exercise is completed in conjunction with a surgical grade pneumatic cuff or tourniquet. Evidence has suggested that BFR assists with muscle hypertrophy, as well lower extremity and upper extremity strength in several populations including athletes, post-operation rehabilitation [5], and the elderly [6]. The clinical value of this technique has been posed to allow increased muscle adaptation and hypertrophy under low loads and intensity that could heretofore only be accomplished with impact activities and more intense training protocols. This is very attractive in a population of early post-operative patients who are not able to engage in this level of activity.

Following ACL reconstruction patients have demonstrated persistent quadriceps strength deficits during and after rehabilitation. Despite there being special attention paid to restoring quadriceps and hamstring strength to pre-operative levels, there is a need for additional intervention. The utilization of BFR in conjunction with current rehabilitation standards of care has shown potential [7]. A meta-analysis completed in 2017 comparing BFR training on musculoskeletal rehabilitation versus traditional low load training, and reported that low load BFR training to be more effective in helping patients regain strength than traditional low load strength training [7]. In a 2018 review of BFR during ACL rehabilitation the authors state the use of BFR as a safe alternative to heavy loads reducing the risk of damage to the graft, cartilage, and meniscus [8]. Current ACSM guidelines for resistance training recommend 70% of a single maximum repetition (RM) to elicit strength and hypertrophy adaptations [9]. BFR provides an alternative to heavy load resistance training due to the light loads prescribed to help reduce mechanical stress on the post-operative knee.

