## Primary aims:

- 1. To determine the relationship between adjunct BFR training during post-surgical rehabilitation and isometric and isokinetic lower extremity strength measures (HUMAC isokinetic dynamometer).
  - a. We hypothesize that there will be a positive association between BFR training and isometric and isokinetic lower extremity strength
- 2. To determine the impact of adding BFR training during post-surgical rehabilitation on functional outcomes.
  - a. We hypothesize that BFR training will improve scores on lower extremity functional tests when compared to a control group.

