### 5. Return to sport testing:

- a. Isometric knee extension at 60 degrees on involved and involved side.
  - i. Quadriceps deficit= 100- (Knee extension peak torque involved/knee extension peak torque uninvolved)
- b. Isometric knee flexion at 60 degrees on involved and uninvolved side
  - i. Hamstring Deficit= 100- (Knee flexion peak torque involved/knee flexion peak torque uninvolved)
- c. Isokinetic knee extension at 300 deg/ sec, 180 deg/sec, and 60 deg/ sec
  - i. Quadriceps deficit= 100- (Knee extension peak torque involved/knee extension peak torque uninvolved)

- d. Isokinetic knee flexion 300 deg/ sec, 180 deg/sec, and 60 deg/ sec
  - i. Hamstring Deficit= 100- (Knee flexion peak torque involved/knee flexion peak torque uninvolved)
- e. Isometric hip extension at 60 degrees on involved and uninvolved side
  - i. Hip extension deficit = 100 (hip extension peak torque involved/ hip extension peak torque uninvolved)
- f. Quad hypertrophy will be measured by thigh circumference measurement.
  - i. Measured at 10cm above the superior pole of the patella bilaterally
- g. Anterior reach test (all measures taken bilaterally)
  - i. 3 trials anterior reach involved and uninvolved (cm)
  - ii. Anterior reach difference= Max anterior reach involved Max anterior reach uninvolved
- h. Single leg heel raise testing (all measures taken bilaterally)
  - i. Maximum number of repetitions completed to maximum height at pace of 60 beats per second
  - ii. Heel raise difference = heel raise involved heel raise non involved
- i. 8" Anterior Stepdown Test (measures taken bilaterally)
  - i. Involved repetitions= Max repetitions in 1 minute.
  - ii. Uninvolved repetitions= Max repetitions in 1 minute.
- j. Half kneeling dorsiflexion (all measures taken bilaterally)
  - i. Half kneeling difference = half kneeling involved- half kneeling non involved
- k. Single leg hop for difference (all measures taken bilaterally)
  - i. Single leg hop difference = maximum involved distance maximum non- involved distance
- 1. Timed hop for distance (all measures taken bilaterally)
  - i. Timed hop difference = time involved time non involved
- m. Single leg triple hop for distance (all measures taken bilaterally)
  - i. Single leg triple hop difference = maximum involved distance maximum non-involved distance
- n. Cross over hop for distance (all measures taken bilaterally)

- o. Cross over hop difference = maximum involved distance maximum non-involved distance

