# Proposed Protocol

## Phase 1- Weeks 1 to 2

- Quad Set: 10 second on, 10 second rest at 100% occlusion x10'
  - progress to isometrics at the edge of the table 60 degrees as clinically appropriate
- Side Lying Hip Abduction, 30/15/15/15, at 80% occlusion
- Hip Extension from prone 30/15/15/15, at 80% occlusion
- Re-check load at the start of each Phase, to determine 1 RM (7-10RM test on leg press)
- Total BFR time approximately 24 minutes per session, with 2 sessions per week

## Phase 2- Weeks 3 to 4

- Replace Quad Set with Long Arc Quad (90-30deg), 30/15/15/15 at 80% occlusion
- Replace Hip Extension with Leg Press (shuttle), 30/15/15/15 at 80% occlusion
- Hip Abduction, 30/15/15/15 at 80% occlusion
- Total BFR time approximately 24 minutes per session with 2 sessions per week

## Phase 3- Weeks 5 to 6

- Long Arc Quad (90-30deg), 30/15/15/15 at 80% occlusion
- Leg Press (shuttle), 30/15/15/15 at 80% occlusion
- Replace Hip Abduction with Bilateral Hip Bridge, 30/15/15/15 at 80% occlusion
- Total BFR time approximately 24 minutes per session, with 2 sessions per week

## Phase 4- Weeks 7 to 8

- Leg Press (shuttle), 30/15/15/15 at 80% occlusion
- Replace Long Arc Quad with Step Up 30/15/15/15 at 80% occlusion
- Bilateral Hip Bridge, 30/15/15/15 at 80% occlusion
- Total BFR time approximately 24 minutes per session, with 2 sessions per week

## Phase 5- Weeks 9 to 12

- Replace Bilateral Hip Bridge with Medial Step Down, 30/15/15/15 at 80% occlusion
- Replace Step up with Split Squat, 30/15/15/15 at 80% occlusion
- Leg Press (shuttle), 30/15/15/15 at 80% occlusion
- Total BFR time approximately 24 minutes per session, with 2 sessions per week

## Phase 6- Weeks 11 to 12

• Progressively load exercises from phase 5

Total BFR time approximately 24 minutes per session, with 2 sessions per week

a. At the conclusion of each exercise completed listed in the proposed protocol above, the following will be recorded:

i) patient rating of perceived exertion (RPE) will be recorded in the exercise flow sheet.

ii) Ability or inability to complete the exercise session

b. At the conclusion of each treatment session any side effect, as previously described by Brandner et al, 2018, will be recorded in the patient chart.

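### The only defined strength outcomes are same-visit deficits against the uninvolved limb, so a group difference in that limb could hide or mimic a BFR effect on the treated limb

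*Combined protocol and SAP*

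**What the plan says.** Primary aim 1 relates BFR training to "isometric and isokinetic lower extremity strength measures", and hypothesis 1a expects a positive association. No specific variable is named.

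The formulas are in sections A) Pre-operative visit, B) 3 month evaluation and 5. Return to sport testing. At 3 months they are "Quadriceps deficit= 100- (Knee extension peak torque involved/knee extension peak torque uninvolved", "Hamstring Deficit= 100- (Knee flexion peak torque involved/knee flexion peak torque uninvolved" and "Hip extension deficit= 100- (Hip extension peak torque involved/hip extension peak torque uninvolved" (each quoted without its closing bracket). The same between-limb form is used at the other two visits. It also serves the isokinetic tests, which appear only at return to sport: "Isokinetic knee extension at 300 deg/ sec, 180 deg/sec, and 60 deg/ sec", with the same speeds for flexion.

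Both limbs are tested, as in "Isometric knee flexion at 60 degrees on involved and uninvolved side". The knee extension line names the involved side twice, apparently a slip, since its formula needs the other limb. Weight and height are among the items collected. No section defines absolute torque, torque per kg, change from the pre-operative visit, or a deficit against the pre-operative uninvolved limb.

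Data Analysis plans t-tests of strength between the BFR and non-BFR groups, again without naming the variable, visit or any baseline adjustment. Prospective controls follow their rehabilitation at an outside facility. In Phase 3 the BFR programme has "Replace Hip Abduction with Bilateral Hip Bridge"; the bridge continues in Phase 4 and is replaced in Phase 5, so it covers weeks 5 to 8.

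**The concern.** A same-visit deficit measures symmetry. It moves when either limb moves. The BFR question concerns the treated limb, so the deficit answers it only if the uninvolved limb is comparable between groups at each visit.

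Nothing in the design secures that. Allocation follows the place of rehabilitation, so training of the uninvolved limb may differ systematically between groups. The bridge is a documented bilateral exercise, and hip extension torque is itself a defined outcome.

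The two errors need opposite conditions:
- If the uninvolved limb is stronger in the BFR group, a real benefit is hidden.
- If it is weaker in the BFR group, for example because outside facilities train it more, a benefit is mimicked.

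Either would give a wrong answer to primary aim 1, and the defined outcomes would not reveal which had happened.

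**Working it through.** The plan gives no strength value, SD, effect size or power, so there is no figure to reproduce.

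**Inputs.** From the documents: the deficit formula, and 33 BFR patients and 14 prospective controls (Study Design). Assumed: control involved/uninvolved ratio r = 0.70 (for example 105 of 150 Nm), varied from 0.6 to 0.9; group differences in the uninvolved limb of 5% to 15%; SD of the deficit 10, 15 or 20 points; two-sided alpha 0.05; 80% power.

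**1. The formula as printed.** At r = 0.70 it gives 100 − 0.70 = 99.3, and at perfect symmetry 100 − 1.00 = 99.0. The evident intention is 100 − 100 × ratio, which gives 30.0 and 0. That form is used below.

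**2. Hiding.** Let the BFR group's involved limb be stronger than the controls' by a fraction g, and its uninvolved limb by u. The apparent benefit (control deficit minus BFR deficit) is 100r × [(1+g)/(1+u) − 1]. Against a fixed reference equal in both groups it would be 100r × g. With r = 0.70 and g = 0.10, the fixed reference gives 7.0 points throughout:

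| Uninvolved limb, BFR v control (u) | BFR deficit | Apparent benefit |
|---|---|---|
| 0% | 23.0 | 7.0 |
| +5% | 26.7 | 3.3 |
| +10% | 30.0 | 0.0 |
| +15% | 33.0 | −3.0 |

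Equal proportional gains in both limbs cancel exactly.

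**3. Mimicking.** With g = 0 and u = −10%, the BFR deficit is 100 − 70/0.90 = 22.2, against 30.0 in controls: a spurious benefit of 7.8 points. With u = −5% it is 3.7 points. For u = −10% the artefact runs from 6.7 points (r = 0.6) to 10.0 points (r = 0.9).

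**4. A change shared by both groups.** Take assumed involved torques of 90 (control) and 100 Nm (BFR), and an uninvolved limb that falls from 150 to 135 Nm in both groups. The deficits are 1 − 90/135 = 33.3% and 1 − 100/135 = 25.9%, a difference of 7.4 points. Against the pre-operative 150 Nm they are 40.0% and 33.3%, a difference of 6.7 points. The contrast survives, so only a differential change does damage.

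**5. Scale.** With 33 v 14, the difference detectable with 80% power is (1.96 + 0.84) × √(1/33 + 1/14) = 0.89 SD, which is 8.9, 13.4 or 17.9 points for SD 10, 15 or 20. A 7.8-point artefact would be declared significant with probability about 0.68, 0.37 or 0.23 respectively (normal approximation, no multiplicity correction).

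**The case against.** The strongest defence is that symmetry is a legitimate measure here. The Introduction motivates the trial with a quadriceps limb symmetry index below 90% and with strength asymmetry at return to sport. The ratio also uses each patient as their own reference for sex, maturity and size, which is valuable in a non-randomised comparison of 12 to 18 year olds. Torque per kg adjusts for mass only. This stands, and it is why the deficit should be kept.

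It is also true that raw torques are collected and that Data Analysis does not restrict itself to the deficit. The deficit is therefore the only defined strength outcome, not a declared primary endpoint.

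Some stronger readings are tempting but unsupported:
- *The uninvolved limb changes during recovery.* No section says so.
- *The BFR programme trains the uninvolved limb generally.* Only the hip bridge is documented as bilateral. The limb trained or cuffed in the leg press and the other exercises is not stated, so for the quadriceps deficit this is inference.
- *Bilateral training could mimic a benefit.* By itself it can only hide one.
- *The Background makes the pre-operative level the trial's endpoint.* The phrase "restoring quadriceps and hamstring strength to pre-operative levels" describes the general focus of rehabilitation.
- *Hypothesis 1a contradicts the deficit.* It speaks of strength, so there is no contradiction, only an unstated direction: a benefit lowers a deficit.

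**Conclusion.** The concern holds in limited form. The defined outcomes cannot distinguish a treated-limb effect from a group difference in the uninvolved limb, and the non-randomised comparison across rehabilitation sites makes such a difference possible. The algebra is certain; whether the limbs differ, and by how much, is not known from the documents.

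Under the stated assumptions, a 10% difference in the uninvolved limb is worth about 7 to 8 points at a ratio of 0.70. That is enough to erase a 10% treated-limb gain or to create an apparent benefit of similar size, but it is below the difference detectable with 80% power at any of the SDs considered. The case is for adding outcomes, not for discarding the deficit. The missing factor of 100 is an error whatever the uninvolved limb does.

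**What to change.** In the three strength-testing sections and in Data Analysis, keep the same-day deficit and prespecify alongside it:

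- **(a)** involved-limb peak torque per kg of test-day body mass, compared between groups with adjustment for the pre-operative isometric value, sex and age where available;
- **(b)** for the isometric tests, involved torque as a percentage of pre-operative uninvolved torque;
- **(c)** uninvolved-limb torque by group.

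State that a deficit difference will be attributed to BFR only if the involved-limb measure agrees. Give the expected direction for each measure: benefit lowers a deficit and raises Nm/kg. Correct the formula to 100 − 100 × (involved/uninvolved), and correct the knee extension line so that it names both limbs.

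**Cost.** No new test is needed, but there are a few more derived variables, and weight must be noted at each strength test. Measure (a) needs a regression model in place of a t-test. The added comparisons must be placed inside the planned multiplicity correction or labelled supportive. The pre-operative reference is unavailable for isokinetic tests, and pre-operative strength is not listed for retrospective controls, so (b) and the baseline adjustment may not be possible for them. Nm/kg does not by itself remove sex or maturity differences, so it should be read together with the deficit.

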### 5. Return to sport testing:

- a. Isometric knee extension at 60 degrees on involved and involved side.
  - i. Quadriceps deficit= 100- (Knee extension peak torque involved/knee extension peak torque uninvolved)
- b. Isometric knee flexion at 60 degrees on involved and uninvolved side
  - i. Hamstring Deficit= 100- (Knee flexion peak torque involved/knee flexion peak torque uninvolved)
- c. Isokinetic knee extension at 300 deg/ sec, 180 deg/sec, and 60 deg/ sec
  - i. Quadriceps deficit= 100- (Knee extension peak torque involved/knee extension peak torque uninvolved)

- d. Isokinetic knee flexion 300 deg/ sec, 180 deg/sec, and 60 deg/ sec
  - i. Hamstring Deficit= 100- (Knee flexion peak torque involved/knee flexion peak torque uninvolved)
- e. Isometric hip extension at 60 degrees on involved and uninvolved side
  - i. Hip extension deficit = 100 (hip extension peak torque involved/ hip extension peak torque uninvolved)
- f. Quad hypertrophy will be measured by thigh circumference measurement.
  - i. Measured at 10cm above the superior pole of the patella bilaterally
- g. Anterior reach test (all measures taken bilaterally)
  - i. 3 trials anterior reach involved and uninvolved (cm)
  - ii. Anterior reach difference= Max anterior reach involved Max anterior reach uninvolved
- h. Single leg heel raise testing (all measures taken bilaterally)
  - i. Maximum number of repetitions completed to maximum height at pace of 60 beats per second
  - ii. Heel raise difference = heel raise involved heel raise non involved
- i. 8" Anterior Stepdown Test (measures taken bilaterally)
  - i. Involved repetitions= Max repetitions in 1 minute.
  - ii. Uninvolved repetitions= Max repetitions in 1 minute.
- j. Half kneeling dorsiflexion (all measures taken bilaterally)
  - i. Half kneeling difference = half kneeling involved- half kneeling non involved
- k. Single leg hop for difference (all measures taken bilaterally)
  - i. Single leg hop difference = maximum involved distance maximum non- involved distance
- 1. Timed hop for distance (all measures taken bilaterally)
  - i. Timed hop difference = time involved time non involved
- m. Single leg triple hop for distance (all measures taken bilaterally)
  - i. Single leg triple hop difference = maximum involved distance maximum non-involved distance
- n. Cross over hop for distance (all measures taken bilaterally)

- o. Cross over hop difference = maximum involved distance maximum non-involved distance
- 6. 12-month testing

Tegner Activity Scale

- 7. Prospective control: All prospective controls will follow the ACL reconstruction protocol at an outside facility. These patients will complete outcome measures, and standardized strength assessments consistent with the standard current standard of care listed above. The same data points will be collected.
- 8. Retrospective controls: Outcome measures (RSI, IKDC) and the results of standardized 3 and 6mo + assessment results will be collected.
- 9. All data points listed above for all three groups will be stored in a Microsoft Excel spreadsheet on the G drive.

## Study Design/Procedures:

The current standard of care for patients undergoing ACL reconstruction at Connecticut Children's and Elite Sports Medicine involves initiation of physical therapy approximately 2-5 days after surgery. All patients undergoing ACL reconstruction follow the surgeon's ACL rehabilitation protocol. Each participant will be evaluated by one of the sport physical therapists during their initial evaluation as part of the current standard of care for all new patients. Patient reported outcomes and strength measurements will be conducted according to the surgeon's protocol for ACL reconstruction patients. The current rehabilitation protocol includes a standardized assessment at 3 months post-operative and 6-9 months post-operative. These assessments help determine progression to the next phase of rehabilitation.

In addition to the standard ACL protocol, patients in this study will utilize the Owen Recovery Science exercise protocol for BFR [18]. The following guidelines will be followed concerning exercise progression, occlusion pressure and difficulties with volume achievement. To determine the appropriate resistance for each exercise, the patient's 1 repetition maximum (1RM) will be attained using a repetition test [19]. This test will use a previously validated algorithm to determine the 1RM based on the weight used to perform a 7-10 repetition test [20]. Patient will perform the exercise with a weight they can comfortably lift for several repetitions. Based on the weight or resistance used, and the patient's perceived exertion a 1RM will be estimated using the modified OMNI-RES scale. The starting load for each exercise will be 20-30% of their 1RM, or bodyweight resistance will be used when loading is not feasible.

Load progression of exercises will be based on the patient's ability to complete the prescribed number of repetitions. If the patient successfully completes all 75 repetitions, they will have their 1 RM reassessed in 1-3 session to increase the load.

If the patient completes between 60-74 repetitions, they will continue with the prescribed training and increase the rest periods between sets 3 and 4, to 45 seconds. They then will continue with the prescribed weight until the patient can complete 75 repetitions for 1 to 3 sessions.

If the patient completes between 45- 59 repetitions, they will continue with the prescribed weight, but will extend the rest period between all sets to 45 seconds. This exercise prescription will be followed until the patient can complete all 75 repetitions. After which the rest periods will be reduced to 30 seconds. Once the Version 12.22.21

patient can complete all 75 repetitions with 30 second break between sets for 1-3 session, they then would have their 1RM reassessed.

If the patient completes less than 44 repetitions, the load will be reduced by approximately 10% until the patient can complete 75 repetitions in the prescribed manor. After the patient has successfully complete 1-3 sessions, they will have their 1RM reassessed using the previously described repetition test.

